9.1 Subjects

Approximately 48 astigmatic subjects will be enrolled with the aim of at least 44 subjects successfully completing the study and being part of the analysis population. Subjects will either be adapted wearers of Avaira Toric lenses, or they will be refit for a minimum of one month lens wear before being refit to Avaira Vitality Toric. Each subject will be required to attend up to five scheduled study visits over a period of approximately two months.

Each subject will be given a unique ID number. All subjects who sign a consent document will be included in the subject enrollment log which will include; subject ID, date of consent, date of screening, date of study completion, date of discontinuation (if req'd), reason for discontinuation (if req'd). (App 20)

Additionally, all subjects must meet the study inclusion and exclusion criteria listed below.

Inclusion criteria

A person is eligible for inclusion in the study if he/she:

- Is between 18 and 40 years of age (inclusive)
- Has had a self-reported eye exam in the last two years
- Is a habitual soft toric lens wearer
- Can be successfully fit with study lenses (\geq grade 2 fit acceptance)
- Has a contact lens spherical prescription between -1.00 to -6.00D with a cylinder between -0.75 and -1.75D (inclusive)
- Has a spectacle cylinder of at least 0.75D in each eye.

- Can achieve best corrected spectacle refraction distance visual acuity of 20/25 (0.10 logMAR) or better in each eye.
- Can achieve a distance visual acuity of 20/30 (0.18 logMAR) or better in each eye with the study contact lenses.
- Has clear corneas and no active ocular disease
- Has read, understood and signed the information consent letter
- Has a contact lens refraction that fits within the available parameters of the study lenses
- Is willing to comply with the wear schedule (at least 5 days per week, > 8 hours/day assuming there are no contraindications for doing so)
- Is willing to comply with the visit schedule.

Exclusion Criteria

A person will be excluded from the study if he/she:

- Has a history of not achieving comfortable CL wear (5 days per week; > 8 hours/day)
- Presents with clinically significant anterior segment abnormalities
- Presents with ocular or systemic disease or need of medications which might interfere with contact lens wear
- Presents with slit lamp findings that would contraindicate contact lens wear such as:
 - Pathological dry eye or associated findings
 - Significant pterygium, pinguecula, or corneal scars within the visual axis
 - Neovascularization > 0.75 mm in from of the limbus
 - Anterior uveitis or iritis (or history in past year)
 - Seborrheic eczema of eyelid region, Seborrheic conjunctivitis
 - History of corneal ulcers or fungal infections
 - Poor personal hygiene
- Has a known history of corneal hypoesthesia (reduced corneal sensitivity)
- Has aphakia, keratoconus or a highly irregular cornea.
- Has presbyopia or has dependence on spectacles for near work over the contact lenses.
- Has undergone corneal refractive surgery.
- Is participating in any other type of eye related clinical or research study.
- Is frequently using rewetting/ lubricating eye drops (more than once per day)

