Study Duration	
The anticipated timeline for this study is as follows:
 
 • Subject enrolment begins: Sept 2016 • Last subject visit anticipated: Jan 2017 • Visits: 
V1: Screening & optimize prescription for Avaira toric V2: Dispense new or optimized prescription Avaira Toric - this visit may not be necessary if subjects habitually wear optimized power Avaira Toric V3: Baseline Avaira Toric & Avaira Vitality Toric dispense V4: 2 week follow-up wearing Avaira Vitality Toric V5: 1 month follow-up wearing Avaira Vitality Toric & Exit

Patient Population	Habitual toric contact lens wearers that provide written informed consent and meet protocol entry criteria.
Sample Size	Target enrollment of 48 subjects with the hope of at least 44 subjects being in the analysis cohort.
Study Center Location (US)	USA
Number of Centers	Multi-Center, 4 sites.

Patient Follow-up	
Patients enrolled in this study will be followed up after the each lens dispensing session. Follow-ups at:
 
 ○ at least 1 month lens wear of Avaira Toric ○ 2-week and 1 month wear of Avaira Vitality Toric
Primary Endpoints	
 • Visual acuity with contact lenses, • Lens fit performance (centration, rotation, blink movement) • Investigator's fit acceptability
[REDACTED]	[REDACTED]

Table of Contents

1	Introduction	8
2	Study Objective	8
3	Study Hypothesis	8
3.1	Study Hypothesis.....	8
4	Study Design	9
5	Study Population	9
5.1	Sample Size Calculation.....	9
6	Investigational Sites	9
6.1	Number of Sites.....	9
6.2	Investigator Recruitment.....	9
7	Ethics Review / Statement of Compliance	10
7.1	Relevant Standards / Guidelines	10
7.2	Institutional Review Board	10
7.3	Clinical Trial Registration	10
7.4	Informed Consent.....	10
8	Potential Risks and Benefits to Human Subjects	10
9	Materials and Methods	11
9.1	Subjects.....	11
	Inclusion criteria	11
9.2	Study Materials.....	13
9.2.1	Contact lens.....	13
9.2.2	Contact Lens care.....	13
9.2.3	Rewetting/ lubricating eye drops	13
9.2.4	Storage of Study Medications/Treatments	13
9.2.5	Clinical Supply Inventory.....	14
9.2.6	Disposal of Consumables	14
9.2.7	Masking and Control of Study Materials.....	14
9.2.8	Ordering and Accountability of Study Materials.....	14
9.3	Visit Schedule and Procedures.....	14
9.3.1	Visit 1: Screening visit & Establish Optimum Prescription	15
9.3.2	Visit 2: Dispense of Avaira Toric Lens.....	18

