9.3.3	Visit 3: Baseline with Avaira Toric & Dispense of Avaira Vitality Toric lenses.....	19
9.3.4	Visit 4: 2-week follow up for Avaira Vitality Toric	21
9.3.5	Visit 5: 1-month follow up on Avaira Vitality Toric Lenses & Study Exit	22

10	Adverse Events and their Reporting	24
10.1	Adverse Response Definitions	24
10.2	Procedures for Adverse Events	26
10.3	Reporting Adverse Events	27
10.4	Discontinuation from the Study	27
11	Statistical Analysis	27
11.1	Statistical analysis	27
12	Data Quality Assurance	28
12.1	Study monitoring	28
12.2	Record keeping	28
12.3	Record retention	28
12.4	Data Entry / Data Management	28
12.5	Confidentiality	29
12.6	Publication	29
13	Study Costs and Subject Compensation	29

1 Introduction

The utilization of soft toric contact lenses has increased significantly over the past few years. CooperVision (CV) produces a number of toric contact lens products including the Avaira toric brand (Enfilcon A) and Avaira Vitality brand (Fanfilcon A). All Enfilcon A toric lenses and Fanfilcon A toric lenses feature CooperVision's exclusive Aquaform® Technology and PEG (Polyethylene Glycol). This combination of material technologies provides a contact lens with high oxygen permeability that is naturally wettable and offers unique comfortable experience.

This study is designed to evaluate how adapted contact lens wearers of Enfilcon A toric lenses will perform following a refit with Fanfilcon A toric lenses, a novel soft contact lens with optimized lens geometry and enhanced water content and UV protection, over one month of daily wear. Overall lens wear experience, including visual quality, lens fit and subjective responses will be assessed.

2 Study Objective

The aim of this study is to determine if adapted contact lens wearers of Enfilcon A toric lenses can be confidently refit into Fanfilcon A toric lenses and be successful after at least one month of daily wear.

Primary outcomes:

- High contrast distance visual acuity (Snellen) with contact lenses
- Lens fit performance (centration, corneal coverage, post blink movement)
- Investigator's fit acceptability

3 Study Hypothesis

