3.1 Study Hypothesis

- Null hypothesis (Ho): There is no difference in lens performance between Enfilcon A toric and Fanfilcon A toric lenses for the key variables measured.
- Alternative hypothesis (H1): There is a difference in lens performance between Enfilcon A toric and Fanfilcon A toric lenses for the key variables measured.

4 Study Design

This is a prospective, multi-center, subject-masked, bilateral wear, two month dispensing study comparing the clinical performance of the Fanfilcon A toric lenses following a refit and adaptation with Enfilcon A toric lenses (Table 1). The subjects will be fit bilaterally into the Enfilcon A toric lenses at the first visit (or continue wearing their habitual Enfilcon A toric lenses) which will be worn for a minimum of one month and then subjects will be re-fit bilaterally with a pair of Fanfilcon A toric lenses for another month of daily wear. After the dispensing Fanfilcon A toric lens, subjects will return for follow up evaluations after 2 weeks, and 1 month.

The subjects will be advised that they may be dispensed with either Enfilcon A toric lenses OR Fanfilcon A toric lenses, however all subjects will be refit with Fanfilcon A toric lenses. The participant will not be informed on which study lens he/she is wearing during the second month but the investigator will have this information.

5 Study Population

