5.1 Sample Size Calculation

A sample size calculation was provided based on the 'subjective comfort just before lens removal' (0-10 scale) data on file at CooperVision from study EX-MKTG-63, which gave a standard deviation of 2.4. For an alpha level of 0.05 and power of 0.8, a sample size of 44 will detect a difference of 1.04, which has been confirmed as acceptable by the sponsor.

We recommend dispensing lenses to at least 48 subjects to be sure to have 44 subjects in the eligible analysis population ie. 12/13 at each of the 4 sites.

6 Investigational Sites

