7.4 Informed Consent

Informed consent (App 18) shall be obtained in writing from the subject and the process shall be documented before any procedure specific to the clinical investigation is carried out.

8 Potential Risks and Benefits to Human Subjects

There may be direct benefits to the subjects in this study, such as improved vision and/or comfort. Participation in a study may contribute to scientific research information that may be used in the development of new contact lens products. In addition, subjects will receive an examination of the front part of their eyes and may have the opportunity to try a different type of soft contact lenses and/or different lens care products at no cost to them. The contact lens materials used in this study are commercially available as daily wear. This study will investigate subjects' wearing schedule intended for daily wear (NOT extended wear), similar to the average wearing time of 10-16 hours for daily wear lenses.

This study is considered to be a non-significant risk study based on United States Food and Drug Administration (FDA) and International Standards Organization (ISO) guidelines, because the study devices used as intended in this study (1) do not represent a potential for serious risk to the health, EX-MKTG-67 v.3.0 Performance of Avaira Vitality Toric Lenses after at least One Month wearing Avaira Toric Lenses (Lavender) 13sep2016

safety or welfare of the subject, and (2) are not implants, (3) are not used to support or sustain human life, (4) are not of substantial importance in diagnosing, curing, mitigating or treating disease or otherwise prevents impairment of human health.

Complications that may occur during the wearing of contact lenses include discomfort, dryness, aching or itching eyes, excessive tearing, discharge, hyperemia and variable or blurred vision. More serious risks may include pain, photophobia, iritis, corneal edema or eye infection. Although contact lens-related infections are very infrequent, the possibility does exist. The incidence of infection due to day-wear soft lenses is 0.035%. Almost always an infection will occur only in one eye. This risk is assumed by 35-million Americans who currently wear contact lenses and only current soft lens wearers will be recruited for this study.

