- For a subject who is a current Avaira Toric wearer but requires a change in prescription, please complete Avaira Toric Prescription Form (App 2B) and schedule Visit 2.
- For a subject who is not a current Avaira Toric wearer, please complete Trial Lens Fitting Form (App 2A) and fit lenses accordingly, after the trial lens fit was successful, complete Avaira Toric Prescription Form (App 2B) and schedule Visit 2.

- Anterior segment ocular health will be assessment (App 4)
 - External Adnexa anomalies (Present/Absent & Describe)
 - Hyperemia
 - Bulbar (0-4, 0.5 steps)
 - Limbal (0-4, 0.5 steps)
 - Palpebral (0-4, 0.5 steps)
 - Cornea & Anterior eye
 - Infiltrates (0- 4, 1 step)
 - Conjunctival infection (0-4, 1 step)
 - EKC (0-4, 1 step)
 - Corneal ulcers (0-4, 1 step)
 - Lens Adhesions (0-4, 1 step)
 - Recurrent Erosions (0-4, 1 step)
 - Other abnormalities (0-4, 1 step)
 - Staining
 - Corneal Staining (0-4, 0.5 step & Optional sketch of staining)
 - Conjunctival Staining (0-4, 0.5 step)
 - Conjunctival Indentation (0-4, 0.5 step)
 - Other findings
- Eligibility Checklist (App 5) will be completed
- Complete Enrolment Log (App 20). If at this point the subject is found to be ineligible, then complete an Exit form (App 13) and exit the subject from the study.

- If a subject is a current Avaira Toric lens wearer and no change to the lens prescription is required then the subject will be instructed to wear the lenses on a daily wear basis, (at least 5 days/week, >8 hours/day), until Visit 3 appointment can be scheduled, unless they experience a problem which warrants lens removal.
- If a subject requires a new prescription for Avaira Toric lenses, please complete the Avaira Toric Prescription Form (App 2B), order the lenses and schedule Visit 2
- If a subject is not a habitual Avaira Toric wearer, re-fit subject into Avaira Toric lens using the Trial Lens Fitting Form (App 2A). After the fit was successful, please complete the Avaira Toric Prescription Form (App 2B), order the lenses and schedule Visit 2.

In some circumstances a repeated Screening may need to be scheduled. Examples include, but are not limited to:

1. Study procedures unable to be completed in time scheduled for visit;
2. Study products not available at the time of the study visit;
3. A transient health condition which may affect the eye(s) (e.g. a common cold, active allergies, fatigue etc.);
4. The short term use of medications (e.g. antibiotics, antihistamines etc.);

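### The entry criteria and Visit 1 routing do not keep out current wearers of the test lens, Avaira Vitality Toric, who would be returned to their own lens as the test condition

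*Combined protocol and SAP*

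**What the plan says.** Section 9.1 sets the habitual-lens requirement as "Is a habitual soft toric lens wearer". The synopsis is equally broad: "Habitual toric contact lens wearers that provide written informed consent and meet protocol entry criteria". The exclusion list in Section 9.1 is printed in full and names no lens brand.

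Section 9.1 then gives two routes: "Subjects will either be adapted wearers of Avaira Toric lenses, or they will be refit for a minimum of one month lens wear" before the test lens is dispensed. Section 9.3.1 applies the same split. Its instruction "For a subject who is not a current Avaira Toric wearer, please complete Trial Lens Fitting Form (App 2A") covers every other brand and has no branch for the test lens. Visit 1 records the brand of the current lens, but the brand is used only for this routing. Under Section 9.3.3, a subject newly fitted with Avaira Toric returns for Visit 3 at least 29 days after Visit 2 and receives Avaira Vitality Toric there.

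The title page classes the study as post-market and the synopsis lists both lenses as approved. Section 8 states: "The contact lens materials used in this study are commercially available as daily wear". On masking, Section 4 says: "The participant will not be informed on which study lens he/she is wearing during the second month". Section 11.1 plans paired t-tests and a binomial test of preference, and gives no subgroup or sensitivity analysis by habitual brand.

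**The concern.** The stated aim (Section 2) is to learn whether adapted Enfilcon A wearers can be refitted into Fanfilcon A and succeed with it. A person who already wears Fanfilcon A by choice cannot help answer that. Their success with the lens was established before enrolment, and the month in Avaira Toric is an interruption of their usual wear.

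Two further consequences follow for such a subject. The mask consists of not telling the subject which lens is worn in the second month, and a habitual wearer may recognise the lens by its feel or handling. Familiarity would also tend to raise comfort scores and preference for the test lens. The order of lenses is fixed and there is no randomisation, so the design does not balance this out, and Section 11.1 does not separate these subjects in the analysis.

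**Working it through.** **Can the subject enter?** Each step follows from the text.

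1. A habitual Avaira Vitality Toric wearer is a habitual soft toric wearer, so the inclusion criterion is met.
2. Table 1 in Section 9.2.1 gives both lenses the same sphere range (-1.00 to -6.00), cylinders (-0.75, -1.25, -1.75) and axes. The prescription criteria therefore do not screen this person out.
3. No exclusion applies.
4. At Visit 1 the person is not a current Avaira Toric wearer, so they are trial-fitted with Avaira Toric and scheduled for Visit 2.
5. At Visit 3, at least 29 days later, they are dispensed Avaira Vitality Toric.

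**The plan's sample size.** Section 5.1 uses comfort just before removal, SD 2.4, alpha 0.05, power 0.8, n = 44 and a detectable difference of 1.04. Reading 2.4 as the SD of the paired difference with a two-sided test, the normal approximation is n = (2.4 × (1.960 + 0.842) / 1.04)² = 41.8. The exact paired t calculation at n = 44 gives power 0.802 and a detectable difference of 1.037. The stated figures reproduce, and this point does not alter them.

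**Effect on the preference test.** Let k be the number of habitual test-lens wearers among 44. The documents do not give k, so a range is shown. Assumptions: each of the k prefers the familiar lens with probability 0.95; each of the other 44 - k is 50:50; all 44 count as one preference or the other; the test is an exact two-sided binomial at 0.05.

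- Critical value: 28 of 44 gives p = 0.096 and 29 of 44 gives p = 0.049, so 29 or more is needed.
- Count for the test lens: Binomial(k, 0.95) + Binomial(44 - k, 0.5).
- Expected share: (0.95k + 0.5(44 - k)) / 44. For k = 4 this is (3.8 + 20) / 44 = 54%.

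| k | Expected share for test lens | Chance of a false significant preference for it |
|---|---|---|
| 0 | 50% | 2.4% |
| 1 | 51% | 3.2% |
| 2 | 52% | 4.2% |
| 4 | 54% | 7.0% |
| 8 | 58% | 17.2% |

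At a milder probability of 0.75, the chance is 4.6% for k = 4 and about 8% for k = 8.

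**Effect on comfort.** If each such subject carries an extra b points towards the test lens, the mean shift is (k/44) × b. With SD 2.4, n = 44 and no true difference otherwise:

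- k = 4, b = 1.04: shift 0.09, two-sided rejection rate 5.8%.
- k = 4, b = 2.0: shift 0.18, rejection rate 7.8%.
- k = 9, b = 2.0: shift 0.41, rejection rate 19.8%.

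**The opposite lean.** Apply the same 0.95 rule to m habitual Avaira Toric wearers, in favour of the control lens. With k = 4 and m = 4, the chance of a false preference for the test lens is 1.6%, below the 2.4% with no habitual lean. With k = 4 and m = 10 it is 0.05%, and the chance of a false preference for the control lens is 9.1%.

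**The case against.** The strongest objection is that the affected group may be empty. Section 1 calls the test lens "a novel soft contact lens with optimized lens geometry", the sponsor supplies it, and Visit 3 waits until it is available. Availability on the market shows that habitual wearers are possible, not that the four sites see them. This stands: with one or two such subjects the effect is negligible. It limits the size of the problem but does not close the gap.

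A reader might infer that the trial as a whole is biased towards the sponsor's new lens. The documents do not support that. Habitual Avaira Toric wearers are eligible by design and may lean the other way, and the calculation above shows that a modest number of them reverses the net direction. They are, however, the intended population, whereas test-lens wearers are not.

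A reader might also infer that the primary endpoints are compromised. These are acuity, lens fit and investigator fit acceptability. No effect of habitual brand on them is shown here. Comfort sets the sample size ("A sample size calculation was provided based on the 'subjective comfort just before lens removal' (0-10 scale) data on file") and preference has its own planned test, but neither is listed as primary.

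Finally, every subject does spend at least 29 days in Avaira Toric, so each undergoes a change from Enfilcon A to Fanfilcon A in the literal sense. Brand is recorded, so affected subjects can be found. The cohort discussion before data export (Section 12.1) could pick them up, but it centres on protocol deviations and adverse events, and an eligible subject is neither.

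**Conclusion.** The gap is real and the severity is low. As written, the plan can enrol a current Avaira Vitality Toric wearer and return that person to their own lens as the test condition. Such a subject contributes nothing to the stated aim, weakens the mask, and would tend to favour the test lens on comfort and preference. Under the assumptions stated, the size runs from nothing (k = 0) to a 17.2% false-preference rate (k = 8 of 44). Both k and the strength of the habit are assumptions, and k may well be zero or small. Neither the net direction of bias over the sample nor any effect on the primary endpoints can be asserted from the documents.

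**What to change.** Add one exclusion to Section 9.1: *Currently wears Avaira Vitality Toric (fanfilcon A) lenses habitually*. Check it against the brand recorded on the screening form (App 1) and confirm it on the eligibility checklist (App 5). Whether to add a look-back period for past wear, and how long, is for the sponsor to set; the documents give no basis for a particular length.

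If such subjects have already been enrolled, repeat the comfort and preference analyses without them as a sensitivity analysis and report how many there were.

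The exclusion uses data already collected and leaves the target at 44 analysed and 48 dispensed. Its cost is a few candidates lost to recruitment. Removing subjects after enrolment costs power instead: at a difference of 1.04, power falls from 0.80 with 44 to 0.78 with 42 and 0.76 with 40.

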9.2 Study Materials

9.2.1 Contact lens

All subjects will have worn, or be fit with an optimized prescription in Avaira Toric for at least one month before being fit and dispensed the Avaira Vitality Toric. Details of the contact lenses are shown in Table 1.

The Avaira Vitality Toric lenses will be provided by the Sponsor. The sites may be asked to source the Avaira Toric lenses as needed and retain invoices for reimbursement.

Table1: Study lenses

Brand	Avaira Toric lenses (Control)	Avaira Vitality lenses (Test)
Manufacturer	CooperVision	CooperVision
Material	Enfilcon A	Fanfilcon A
Water Content	46%	55%
Base Curve	8.5	8.4
Lens Diameter	14.5	14.2
Lens Powers Sphere	-1.00 to - 6.00 (0.25 steps)	-1.00 to - 6.00 (0.25 steps)
Lens Power Cylinder	-0.75, -1.25, -1.75	-0.75, -1.25, -1.75
Axis	10 ^o to 180 ^o (10 ^o steps)	10 ^o to 180 ^o (10 ^o steps)
Replacement schedule	Daily wear	Daily wear

